10.3 Analysis Plan

Each outcome measure will be analyzed for the intent-to-treat population. All statistical tests will be conducted at the 5% Type I error rate (two-sided). All regressions will use outcome as the response variable, treatment (TOME vs. Control) as the covariate of interest, and baseline outcome as a supporting covariate. Site and site-by-treatment will be initially included as supporting covariates and dropped if they are not significant. Baseline-Week-3 continuous outcomes such as the difference in MOUD knowledge will be tested using linear regressions. The Pearson Chi-Square test will be used to test for treatment group differences in AEs.

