3.6 Primary Analysis

Baseline-Week-3 difference in MOUD knowledge will be tested using linear regression at the 5% Type I error rate (two-sided) for the intent-to-treat population.

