6.4 Site and Participant Selection

6.4.1 Site Selection

CTN is conducting the Medication treatment for Opioid-dependent expectant Mothers (MOMs; CTN-0080²³) trial to compare mother and infant outcomes of pregnant persons with OUD treated with extended-release buprenorphine (BUP), relative to sublingual BUP. CTN-0080 has completed recruitment but has a very long active treatment phase (i.e., through 12 months postpartum). Staff need to be retained through the CTN-0080 active treatment phase. The proposed study would be conducted with six CTN-0080 sites with sufficient census to enroll randomize approximately four participants per month.

6.4.1.1 *Site Characteristics*

Participating sites should:

1. have been a site in CTN-0080;
2. have sufficient census to meet the target randomization of 4 per month

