8.4 Randomization Plan

Eligible participants will be randomized in a 1:1 ratio, stratified by site, to TOME or Control. Research staff will randomize participants to the TOME or Control arm, using REDCap's randomization module; the randomization sequence will be unknown to the research staff.

Table 1: Overview of Assessments and Procedures			
Research Visits	Screen/baseline/ randomization	Week 3 visit	As Needed
Screening Assessments			
Pre-screen interview	X		
Informed Consent	X		
Demographics	X		
Treatment and Perinatal Status	X		
Prisoner Status	X		
PRISM-Suicide/Homicide	X		
Sample Characteristics			
Substance use history	X		
Safety Assessments			
Adverse events		X	
Efficacy Assessments			
Opioid Overdose and Treatment Awareness Survey (OOTAS)	X	X	
Methadone Maintenance Treatment Stigma Mechanisms Scale (MMT-SMS)	X	X	
Thoughts about abstinence	X	X	
Administrative Forms			
Locator information form	X		
Study Eligibility	X		
Study Intervention Provided	X		
Study Completion			X
Protocol Deviation			X
Mental Health Follow-up Assessment			X

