10.0 ANALYTICAL PLAN

10.1 Statistical Hypotheses for Primary Objective

10.1.1 Key Hypotheses

It is hypothesized that the TOME, relative to the control, group will have a greater increase in: 1) MOUD knowledge (primary); and 2) opioid-overdose knowledge (key secondary).

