10.4 Sample Size Analysis

In our published PTOEND pre-post study we were able to detect a statistically significant increase in opioid-overdose and MOUD knowledge with 80 enrolled participants.⁵ In an unpublished pre-post evaluation of the MOUD education component in patients recently enrolled in MOUD (either buprenorphine or methadone), a sample size of 40 was sufficient to detect a statistically significant increase in mean correct responses from baseline (6.1, SD=1.5) to post-PTOEND (7.3, SD=1.1). Assuming a two-sided test, an $\alpha = .05$, that $\geq 88\%$ of enrolled participants attend the week 3 visit, and mean correct post-intervention responses of 7.3 for the TOME and 6.7 for the Control group, the target sample size of 120 will provide 80% power to detect the difference as statistically significant.

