10.6 Minority/Sex Analyses

In accordance with National Institutes of Health guidelines, modelling of the key outcomes will be completed to determine whether treatment response was significantly affected by participant minority status using an interaction term between treatment arm and minority status being considered.

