16.3 Data Management and Analysis

1. **Data acquisition and transmission:** Information will be obtained through REDCap, a web-based electronic data capture and management system. All research staff will be trained in Good Clinical Practice (GCP) guidelines. All data will be de-identified. Only research staff members directly involved with the study will have access to identifying information for the participants.
2. **Data entry methods:** De-identified demographic and clinical data will be managed in REDCap, a software toolset and workflow methodology for collection and management of clinical research data developed by Vanderbilt University, in collaboration with institutional partners including the University of Cincinnati Academic Health Center. Only the necessary study personnel will have access to the database.
3. **Data analysis plan:** All analyses will be completed on the intent-to-treat (ITT) sample using SAS, Version 9.4 (SAS Institute, Inc.). Statistical tests will be conducted at a 5% Type I error rate (two-sided) for all measures. No interim efficacy analyses or adaptive features are planned.

4. Efficacy Analyses:

Each outcome measure will be analyzed for the intent-to-treat population. All statistical tests will be conducted at the 5% Type I error rate (two-sided). All regressions will use outcome as the response variable, treatment (TOME vs. Control) as the covariate of interest, and baseline outcome as a supporting covariate. Site and site-by-treatment will be initially included as supporting covariates and dropped if they are not significant. Baseline-Week-3 continuous outcomes such as the difference in MOUD knowledge will be tested using linear regressions. The Pearson Chi-Square test will be used to test for treatment group differences in AEs.

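### Site terms stay or go by significance test, and the plan does not say what the overall TOME effect is if site-by-treatment stays

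*Combined protocol and SAP*

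**What the plan says.** Section 10.3 regresses each outcome on treatment, as the covariate of interest, with the baseline value as a supporting covariate. It then adds: "Site and site-by-treatment will be initially included as supporting covariates and dropped if they are not significant". Section 16.3 repeats the rule. Neither gives a separate level for these selection tests; the general two-sided 5% level appears to apply.

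The related passages are:

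- Section 8.4: "Eligible participants will be randomized in a 1:1 ratio, stratified by site, to TOME or Control".
- Section 10.1.1: "It is hypothesized that the TOME, relative to the control, group will have a greater increase in: 1) MOUD knowledge (primary"). This compares whole groups, so a trial-wide effect is the likely intent.
- Section 16.3: "All analyses will be completed on the intent-to-treat (ITT) sample using SAS, Version 9.4". No procedure, coding or contrast is named.
- Section 3.6, the synopsis, describes one linear regression at the two-sided 5% level and mentions no site terms.
- Section 6.5 rests the case for a follow-up trial on two significant results, for MOUD knowledge and for stigma. Both regressions fall under the rule.

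**The concern.** There are two points, of unequal weight.

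**(a) The effect is undefined if the interaction stays.** Without the interaction, the treatment coefficient is the trial-wide effect. With it, there are about six site-specific effects, and the coefficient labelled treatment depends on the coding. Under reference-site coding it is the effect at one site. A trial-wide effect needs stated weights, such as equal, by site size or by precision. The plan says when the interaction is kept but not what is tested next, so that choice would be made with the data in hand.

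**(b) The stratification factor can be dropped.** Randomization is stratified by site, yet site remains in the analysis only if it is significant. The primary model is therefore not fixed until the data are seen.

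At stake is how clearly the primary result, and the stigma result used beside it in section 6.5, is defined in advance. The sample size is not at stake.

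**Working it through.** **1. The plan's own power figure.** Section 10.4 states that "the target sample size of 120 will provide 80% power to detect the difference as statistically significant". The inputs there are means of 7.3 and 6.7 (difference 0.6), at least 88% attendance and two-sided α = 0.05. The SD used is not stated. Of the two SDs quoted, 1.1 (post-intervention) reproduces the figure and 1.5 (baseline) gives 54%.

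- Completers per arm: 120 × 0.88 / 2 = 52.8
- SE = 1.1 × √(2/52.8) = 0.214
- Power = Φ(0.6/0.214 − 1.96) = 0.800. A t-test with 53 per arm gives 79.4%.

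The stated 80% reproduces.

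**2. Two readings of the treatment effect with the interaction kept.** Take six equal sites, so 52.8/6 = 8.8 per arm per site.

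- Reference-site coefficient: SE = 1.1 × √(2/8.8) = 0.524, and power for a 0.6 difference is 0.21.
- Equal-weight average of six site effects: SE = 0.524/√6 = 0.214, the same as in step 1.

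The same fitted model thus gives a standard error 2.4 times larger (0.524/0.214) under one reading than under the other.

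**3. The whole rule, simulated with no true interaction.** There were 40,000 runs per scenario (Monte Carlo SE about 0.11 points for type I error and 0.2 for power).

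- Completers: 106, in sites of 18/18/18/18/17/17. This follows the common site requirement in section 6.4.1 to "have sufficient census to meet the target randomization of 4 per month".
- SD: 1.1 within site.
- Tests: interaction first at 5%, then site.
- Assumed, because the documents give no values: baseline–outcome correlation r of 0 or 0.4, and between-site SD of 0 or 0.35.

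The comparator is a fixed model with treatment, baseline and site. The interaction was kept in 4.6–5.2% of trials.

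| | Fixed model | Rule, equal-weight site average | Rule, reference-site coefficient |
|---|---|---|---|
| Type I error | 4.9–5.0% | 5.0–5.1% | 5.9–6.0% |
| Power, r = 0 | 78.7–79.2% | within 0.4 points of fixed | 76.7–76.9% |
| Power, r = 0.4 | 85.4% | within 0.4 points of fixed | 83.0–83.2% |

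**4. Uneven sites.** With an assumed 34/24/18/13/10/7 and r = 0.4, type I error is 4.8–5.1% (fixed), 5.1–5.3% (equal-weight) and 5.8–6.0% (reference-site). Power loss against fixed is 0.4–0.9 points (equal-weight) and 1.7–3.0 points (reference-site).

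**5. If site effects truly differ.** The documents give no between-site SD of the treatment effect, so 0.3 and 0.6 are assumptions, and 0.6 equals the whole planned effect. This used 20,000 runs per setting, near-equal sites and no baseline covariate.

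| SD of effect | Interaction kept | Type I error, reference-site vs fixed | Power, reference-site vs fixed |
|---|---|---|---|
| 0.3 | about 13% | 7.5% vs 4.7% | 73% vs 79% |
| 0.6 | about 42% | 16% vs 4.2% | 62% vs 78% |

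In a parallel run with six equal sites, 108 completers and an effect SD of 0.6, the equal-weight average held type I error at about 5% and power at about 80%.

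**6. Two outcomes.** With no true interaction, the chance that at least one of the knowledge and stigma models keeps it lies between 5% (fully correlated) and 1 − 0.95² = 9.75% (independent). This is not an error rate. It is how often the effect to report would be left open.

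**7. Point (b).** With between-site SD 0.35, site is dropped in 40–47% of the trials where the interaction is dropped. Power under the rule with the site average still equals the fixed model: 79.2% vs 79.2% at r = 0, and 85.4% vs 85.4% at r = 0.4.

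**The case against.** The strongest reply is that the measurable harm needs a reading the plan does not suggest. Treatment is the covariate of interest and the hypothesis compares whole groups, so a competent analyst would average over sites. With near-equal sites, almost nothing then changes. Even with the uneven sites above, a size-weighted average removes the loss: power is 86.0% vs 85.5% for the fixed model with no site differences, and 85.8% vs 85.9% with between-site SD 0.35. A drop rule at a stated level is also itself pre-specified. The trial is a pilot, and section 6.5 is not a formal gate. The synopsis's silence on site proves little, since it omits the baseline covariate too.

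Most of this stands, and it limits the size of the point. The larger figures in step 5 need both a reference-site coefficient and an assumed spread of effects. Point (b) shows no numerical harm.

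The objection does not supply the missing definition. The plan does not say that an average is used, or which one. The choice of weights is not neutral: with the uneven sites and a true average difference of 0.6, equal-weight and precision-weight tests disagreed on significance in about 25% of the trials that kept the interaction.

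**Conclusion.** The concern holds, at modest size. The text lets significance tests set the site terms in the primary model and leaves the trial-wide effect undefined if the interaction is kept.

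With no true interaction, that happens in about 5% of trials per outcome. A site-averaged contrast makes it nearly harmless. A reference-site coefficient raises type I error to about 6% and costs 2.0–2.5 power points with near-equal sites. Larger effects arise only if site effects really differ, on which the documents give no figure.

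Dropping site matters only because it leaves the model unfixed. These results assume about six sites, 88% attendance and an inferred SD of 1.1. The change is worth making because it costs almost nothing, not because the design is at risk.

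**What to change.** Replace the sentence in sections 10.3 and 16.3 with:

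> The model for each outcome includes treatment, baseline score and site as fixed effects, regardless of significance. The primary test is of the treatment effect in this model. Site-by-treatment is examined only in a separate exploratory model, with site-specific estimates and confidence intervals.

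This analyses by the factor used in randomization. It also fits section 10.6, which appears to treat the minority-status interaction as an analysis of its own, asking "whether treatment response was significantly affected by participant minority status using an interaction term between treatment arm and minority status".

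The cost is one sentence in two places and 5 of about 100 degrees of freedom. With no site differences, always fitting site instead of never fitting it took power from 78.9% to 78.7% at r = 0 and from 85.5% to 85.4% at r = 0.4. The sample size is unchanged. Site-specific estimates will be imprecise at about 18 completers per site and should be labelled descriptive.

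A smaller alternative is to keep the rule and add one clause naming the contrast and site weights to be used if the interaction is kept. That settles point (a) but not point (b).

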6.4.2 Participant Selection

6.4.2.1 *Inclusion Criteria*

Potential participants must be:

1. 18 years of age or older;
2. pregnant or be within 12 months postpartum;

3. enrolled in MOUD (either buprenorphine or methadone) at the study site or affiliated clinic where enrollment can be confirmed;
4. able to understand the study, and having understood, provide written informed consent in English

6.4.2.2 *Exclusion Criteria*

[figure not shown]
Potential participants must not:

1. have suicidal or homicidal ideation requiring immediate attention
2. be currently in jail, prison, or any inpatient overnight facility as required by court of law or have pending legal action

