7.3 Safety Measures of the Primary Objective

7.3.1 Adverse Events (AEs)

There are not specific guidelines for adverse event (AE) and serious adverse event (SAE) reporting for behavioral trials but it is important to assess for potential AEs that could result from exposure to a behavioral intervention.²⁶ TOME is a low-risk intervention but staff will assess for two AEs that would be of clinical import: 1. Suicidal ideation and 2. Homicidal ideation. Research suggests that using the FDA definition of SAEs (i.e., an adverse event that results in any of the following outcomes: death; life threatening; requires hospitalization, initial or prolonged; results in disability; congenital anomaly; requires intervention to prevent permanent impairment or damage; or other significant medical event) for behavioral trials with substance using populations does not produce meaningful safety information in that many SAEs are reported but none judged to be related to the intervention.²⁷ SAEs will only be reported for events related to a study-defined AE (e.g., hospitalization due to suicidal ideation, etc.).

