7.4 Other Measures

7.4.1 Screening Assessments

Pre-screen Interview: The pre-screen interview will include questions about pregnancy/postpartum status and enrollment in MOUD treatment.

Demographics: Items from the PhenX Tier 1 of the Substance Abuse and Addiction core²⁸ will be used to collect information on demographic characteristics.

Suicidal and Homicidal Screening Form (PRISM): The Suicide and Homicide Screening Form is a structured, reliable interview modified from the Psychiatric Research Interview for Substance and Mental Disorders- PRISM²⁹ and will be completed by study staff during screening/baseline. A qualified mental health professional must assess participants reporting current suicidal/homicidal intent as specified in the site clinical SOP. For visits held via telemedicine or at an external location, research staff will contact a qualified clinician via phone to coordinate an assessment via telemedicine as quickly as possible; ideally this assessment will occur while the staff and participant are together at the external location.

Treatment and Perinatal Status: The Treatment and Perinatal Status form will be used to assess study candidates' status on study inclusion/exclusion criteria related to pregnancy / postpartum status and enrollment in MOUD treatment.

Prisoner Status: The Prisoner Status form will be used to assess study candidates' status on the study exclusion criterion related to prisoner status.

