Mental Health Follow-up Assessment: This assessment must be completed by a qualified clinician if the participant endorses suicidality or homicidality in response to the AE assessment. The completion of the Mental Health Follow-up Assessment form requires direct evaluation of the participant for suicide/homicide risk by a qualified mental health professional according to the site's specific SOP. This evaluation will ideally take place prior to the participant leaving the study visit. For visits held via telemedicine or at an external location, research staff will contact a qualified clinician via phone to coordinate an assessment via telemedicine as quickly as possible; ideally this assessment will occur while the staff and participant are together at the external location.

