2. **Collection and management of AEs and SAEs:** In general, the risks associated with trials employing behavioral interventions are presumed minimal relative to those evaluating pharmacologic interventions. An adverse event (AE) for this trial testing a low risk, education intervention is defined as: 1. Suicidal ideation and 2. Homicidal ideation.

SAEs will only be reported for events related to an AE (e.g., hospitalization due to suicidal ideation, etc.). We will use FDA criteria for SAEs (i.e., an adverse event that results in any of the following outcomes: death, life threatening event, initial or prolonged hospitalization, disability, congenital anomaly, intervention to prevent permanent impairment or damage, or other significant medical event). The study staff will be trained to monitor for and report AEs and SAEs. Additionally, as applicable, sites will submit reporting of AEs/SAEs according to IRB requirements. Each of the sites has established practices for managing medical and psychiatric emergencies, and the study staff will continue to utilize these procedures. Treatment providers at each site will be responsible for monitoring participants for possible clinical deterioration or other problems, and for implementing appropriate courses of action.

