16.8 DSM Plan Administration

1. **Responsibility for data and safety monitoring:** Site study staff will be responsible for the clinical management and safety monitoring of the study participants.

2. Frequency of DSM reviews: Breaches of confidentiality will be reviewed by study leadership in regularly scheduled meetings for the duration of the study.
3. Content of DSM report: The DSM report, which will be contained in the final study report, will include a brief description of the study and any changes made. Additionally, we will report baseline sociodemographic characteristics, including age and race of the participants screened and randomized. We will also report retention rates and the disposition for all study participants. Any quality assurance issues, regulatory issues, and breaches of confidentiality will be included in the report.

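### Does the adverse-event comparison need a rule for ideation that was already present at baseline?

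*Combined protocol and SAP*

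**What the plan says.** Section 10.3, repeated in the efficacy-analysis text of section 16.3, plans one between-arm safety test, two-sided at 5%: "The Pearson Chi-Square test will be used to test for treatment group differences in AEs". The baseline-covariate rule in the same paragraph covers the regressions and does not reach this test.

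Section 16.6 defines the event: "An adverse event (AE) for this trial testing a low risk, education intervention is defined as: 1. Suicidal ideation and 2. Homicidal ideation". Sections 7.3.1 and 11.16.2 name the same two events. None of the three says new, worsened or since baseline. Section 7.3.1 does give the purpose: "it is important to assess for potential AEs that could result from exposure to a behavioral intervention".

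At entry, section 6.4.2 excludes only candidates who "have suicidal or homicidal ideation requiring immediate attention". The PRISM suicide/homicide form is completed at screening/baseline. Table 1 in section 8.4 schedules that form at baseline only and the AE assessment at Week 3 only. Section 7.5 gives the trigger for the mental health follow-up form: "This assessment must be completed by a qualified clinician if the participant endorses suicidality or homicidality in response to the AE assessment".

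**The concern.** A participant may have non-urgent ideation at randomization and report the same ideation three weeks later. Under the literal definition in section 16.6 that is an adverse event. Under the purpose in section 7.3.1, events that could result from exposure, it arguably is not. The plan therefore permits two event counts and does not choose between them.

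Continuing cases that fall equally in both arms add noise without adding to the difference, so the all-cases count could hide a rise in new ideation. This is the only between-arm safety test. Sections 11.16.1 and 16.9 set up no separate DSMB, and the content list for the DSM report in section 16.8 does not name adverse events. The trial is open-label, so a rule left open could in principle be settled after arm-level results are visible. What is at stake is the reported safety conclusion. The primary outcome is not affected.

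**Working it through.** **Inputs from the documents.** 120 randomized 1:1 (sections 6.2 and 8.4), so 60 per arm. At least 88% attend Week 3 (section 10.4): 0.88 × 60 = 52.8, about 53 per arm. Two-sided 5% (section 10.3).

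**The plan's own figure.** Section 10.4 states 80% power for MOUD knowledge. With means 7.3 and 6.7, SD 1.1 and 52.8 per arm, the standardized difference is 0.6 / (1.1 × √(2/52.8)) = 2.80, and Φ(2.80 − 1.96) = 0.80. It reproduces. No power is stated for the adverse-event test.

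**Inputs not in the documents (assumed).** q = share with ideation at baseline; r = share of those still reporting it at Week 3; p = share of the others who newly report it.

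**Formulas.** Event probability per arm:
- new cases only: (1 − q)p
- all Week-3 cases: rq + (1 − q)p

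Power is the sum of binomial probabilities over all 2×2 tables that the uncorrected Pearson test rejects, with 53 per arm.

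**1. Equal persistence, large effect.** p = 12% vs 2%, r = 70% in both arms. At q = 10% the event probabilities are 0.108 vs 0.018 (new) and 0.178 vs 0.088 (all).

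| q | new only | all |
|---|---|---|
| 5% | 0.515 | 0.369 |
| 10% | 0.489 | 0.271 |
| 20% | 0.435 | 0.180 |

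At 60 per arm and q = 10%: 0.55 vs 0.30. So a loss of about half can occur, but it takes a six-fold rise in new ideation and persistence that is the same in both arms.

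**2. Equal persistence, smaller effects.** q = 10%, r = 70%.

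| p, TOME vs Control | new only | all |
|---|---|---|
| 5% vs 2% | 0.087 | 0.073 |
| 4% vs 2% | 0.050 | 0.060 |
| 3% vs 1% | 0.034 | 0.060 |

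The test has almost no power under either count.

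**3. Persistence differs by arm.** r = 90% on TOME and 50% on Control. At q = 10% and p = 12% vs 2%, the all-cases probabilities are 0.09 + 0.108 = 0.198 and 0.05 + 0.018 = 0.068.

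| q | p, TOME vs Control | new only | all |
|---|---|---|---|
| 10% | 12% vs 2% | 0.489 | 0.513 |
| 20% | 12% vs 2% | 0.435 | 0.559 |
| 20% | 2% vs 2% | 0.009 | 0.201 |

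The ranking reverses. In the last row the only harm is to participants who already had ideation, and the new-only count cannot see it.

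**4. Validity.** With no effect, q = 10%, p = 5% and r = 70% in both arms, the rejection rate is 0.043 for new cases and 0.049 for all cases. Either count alone holds its level.

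**5. One data set under both counts.** Pearson X² = 106 × (ad − bc)² / (53 × 53 × events × non-events).
- 7 vs 1 new cases: 106 × (7×52 − 1×46)² / (53 × 53 × 8 × 98) = 4.87, p = 0.027.
- Four continuing cases added to each arm, 11 vs 5: 106 × (11×48 − 5×42)² / (53 × 53 × 16 × 90) = 2.65, p = 0.104.

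The two counts can fall on opposite sides of 0.05. But 7 vs 1 has an expected count of only 4 events per arm, and Fisher's exact p is 0.060, so that result is fragile whichever cases are counted.

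**The case for a change.** The strongest case for a change is that the purpose in section 7.3.1 points to ideation arising after exposure, and that a few sentences fixing a new-only rule would cost almost nothing. With equal persistence and a six-fold rise in new ideation, the two counts disagree on significance in 27%, 33% and 37% of simulated trials at 5%, 10% and 20% baseline ideation. If an analyst could pick whichever count was significant, the false-positive rate with no true effect would be 7.6% to 8.4% at 5% new ideation, and 5.4% to 5.7% at 2%.

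The omission and these figures stand. The preference for new cases does not follow from them. It assumes that the intervention cannot affect people who already have ideation, who are arguably the most vulnerable. A new-only rule would move continuing or worsened ideation to an untested row, so the plan would lose a harm that its test can now detect. The rule also depends on the baseline form recording ideation. Section 7.4.1 states only this: "A qualified mental health professional must assess participants reporting current suicidal/homicidal intent as specified in the site clinical SOP". The documents do not say outright whether ideation short of intent is captured.

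The excess from picking a count is at most about 3.4 percentage points (8.4 − 5.0) in the settings examined, and nothing in the documents suggests that such a choice is intended. The section 16.8 list does omit adverse events; it ends with "Any quality assurance issues, regulatory issues, and breaches of confidentiality will be included in the report". But section 16.5 has study-defined AEs and SAEs entered in a database, and SAEs reported to the IRB and NIDA within 72 hours, so the events are not lost from view.

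**Conclusion.** No change to the plan is needed. The documents do not say whether baseline ideation that continues to Week 3 counts as an event, or which denominator applies. That is a missing detail, and filling it either way involves a fair trade-off. New cases only is more sensitive to new onset when persistence is equal across arms. All Week-3 cases is more sensitive when the intervention affects persistence. Each is a valid randomized comparison.

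No general loss of power can be claimed. In the settings above, the ratio of all-cases to new-only power runs from 0.41 (0.180/0.435, equal persistence, q = 20%) to 1.28 (0.559/0.435, unequal persistence, q = 20%) when new ideation is 12% vs 2%. At 5% vs 2% with 10% baseline ideation and equal persistence, neither count exceeds 0.09. With no baseline ideation the two counts coincide. All of this rests on assumed rates, since the documents give none.

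The consequence is small. The plan ties no stopping decision to this test, and the primary and key secondary analyses are untouched. A competent analyst would show new and any Week-3 ideation side by side by arm, as far as the baseline form allows, with the number lacking a Week-3 assessment. Stating the rule before arm-level data are seen would be a courtesy to readers; it would not correct an error.

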6.2 Number of Sites and Participants

Approximately 120 participants, recruited from approximately 6 sites, will be randomized into the trial. Patients enrolled in MOUD (either buprenorphine or methadone) at the study site who are either pregnant or within 12 months postpartum will be recruited for the study. Participants may be recruited from a variety of other sources, including advertising if needed. Recruitment advertisements will be approved by the Institutional Review Board (IRB). Efforts will be made to recruit a study sample that reflects, or exceeds, the proportion of minorities in treatment at the sites.

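### The only between-arm safety analysis is a chi-square p-value, which at about 53 to 60 per arm cannot show how much extra ideation remains possible; a risk difference with an interval should lead

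*Combined protocol and SAP*

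**What the plan says.** Section 10.3 gives the comparison of adverse events one sentence, "The Pearson Chi-Square test will be used to test for treatment group differences in AEs", and sets every test at two-sided 5%. Section 16.3, item 4, repeats it. Neither place mentions a risk difference, a confidence interval, what to do when counts are small or zero, or the denominator for adverse events.

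Section 16.6 narrows what counts: "An adverse event (AE) for this trial testing a low risk, education intervention is defined as: 1. Suicidal ideation and 2. Homicidal ideation". Serious events are collected only if linked to one of these (7.3.1, 11.16.2, 16.6). Section 6.4.2 bars entry to people who "have suicidal or homicidal ideation requiring immediate attention". Table 1 in 8.4 schedules the adverse event assessment at the Week 3 visit only.

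On size, section 6.2 says "Approximately 120 participants, recruited from approximately 6 sites, will be randomized into the trial", and section 8.4 says "Eligible participants will be randomized in a 1:1 ratio, stratified by site, to TOME or Control". Section 10.4 assumes that at least 88% "of enrolled participants attend the week 3 visit". The listed contents of the monitoring report in 16.8 include no adverse event summary.

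**The concern.** A p-value alone answers one question: could the observed split be chance? In a small trial with rare events the answer will usually be yes, whether or not the intervention does harm. A reader of the safety results needs to know how large an excess of ideation the data still allow, and nothing planned supplies that.

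Section 16.6 already describes the education intervention as safe in earlier studies and says that promising results would support a larger trial. In that setting a bare non-significant result could easily be read as reassurance it does not contain. If nobody has an event, the planned test yields no result at all.

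**Working it through.** **Inputs.** Total 120, allocated 1:1, so 60 per arm (6.2, 8.4). With 88% attendance, 0.88 × 60 = 52.8, about 53 per arm (10.4). Two-sided 5% (10.3). The documents give no ideation rate, so the rates below are assumptions. I count a participant with either kind of ideation as one event, because the plan does not say whether the two are pooled.

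**The plan's own power figure.** Section 10.4 states 80% power for the primary outcome, with means of 7.3 and 6.7. Its power sentence names no SD; I use the post-education SD of 1.1 given just before it. Then 0.6 / (1.1 × √(2/53)) = 2.81, and Φ(2.81 − 1.96) = 80.2% (79.4% with the t distribution). The figure reproduces, which supports 53 per arm as the planning size. No power is stated for adverse events.

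**Expected counts.** Five expected events per arm need a rate of 5/53 = 9.4%, or 5/60 = 8.3%. At 53 per arm, rates of 1%, 2%, 5% and 8% give 0.5, 1.1, 2.7 and 4.2 events; 10% gives 5.3.

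**When the test can reject.** With n per arm and x v y events, Pearson's statistic is X² = 2n(x − y)² / [(x + y)(2n − x − y)], compared with 3.84. At n = 53:
- 0 v 0: 0/0, undefined.
- 3 v 0: 106 × 9 / (3 × 103) = 3.09, p = 0.079. With three or fewer events in total, no split reaches 5%.
- 3 v 1: 106 × 4 / (4 × 102) = 1.04, p = 0.31.
- 4 v 0: 106 × 16 / (4 × 102) = 4.16, p = 0.041.

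**Chance that the test is undefined.** At a common rate r this is (1 − r)^106: 0.99^106 = 34% at 1%, and 0.98^106 = 12% at 2%.

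**Power.** Sum the two binomial probabilities over every table with X² > 3.84, counting 0 v 0 as no rejection.

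| True rates (one arm v other) | 53 per arm | 60 per arm |
|---|---|---|
| 4% v 2% | 6% | 7% |
| 6% v 2% | 15% | 18% |
| 10% v 5% | 15% | 17% |
| 10% v 2% | 41% | 46% |

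At 53 per arm, 80% power is reached at about 16.7% v 2%. At 60 per arm, 15% v 2% has 78%.

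**Type I error.** The same sum with equal rates, at 53 per arm, gives 0.2%, 1.5%, 4.4% and 4.8% at rates of 1%, 2%, 5% and 8%. The maximum over all rates is 5.3% (5.5% at 60 per arm).

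**What an interval would show.** The Miettinen-Nurminen 95% interval holds every difference d with (observed difference − d)² / V(d) ≤ 3.84. Here V(d) is the variance at the rates fitted under d, times N/(N − 1), with N = 2n.
- 0 v 0: the fitted rates are d and 0, so the limit solves d = 3.84 / (3.84 + n(N − 1)/N). At n = 53, 3.84 / (3.84 + 52.5) = 6.8 points. At n = 60, 3.84 / (3.84 + 59.5) = 6.1 points.
- 3 v 1 at n = 53: the observed difference is 2/53 = 3.8 points, and the interval, solved numerically, is −5.0 to +13.8 points. The planned output would be p = 0.31 alone.

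**The case against.** **The sparse-event premise is assumed.** This stands. The documents give no rate, and 6.4.2 excludes only ideation that needs immediate attention, so lesser ideation can enter and be counted. Above about 8% to 9% the expected counts are adequate. The low power does not depend on sparse counts, though: 10% v 5% has only 15%.

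**Naming a test does not forbid showing counts, and serious events are handled separately.** Section 16.5 requires serious events to be reported within 72 hours, and 11.16.1 allows an ad hoc board meeting. Both are monitoring of individual events, not a comparison of arms. Nor does any section say that the safety conclusion will rest on the p-value; misreading it is a reporting risk that the plan leaves open.

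**A reader might infer that Pearson's test is invalid here and produces false alarms.** At 53 per arm it does disagree with Fisher's test: 4 v 0 gives 0.041 v 0.118, and 8 v 2 gives 0.046 v 0.093. Given exactly four events and no effect, it rejects 11.8% of the time. But the design does not fix the total, the rate is zero at one to three events, and the overall size stays near or below 5%. Barnard's test agrees with Pearson at both splits (0.043 and 0.049), while Boschloo's does not (0.087 and 0.064). The score interval at 4 v 0, +0.5 to +17.9 points, also excludes zero. Choosing among these tests is a trade-off, and Fisher's would lower the power further (4% for 6% v 2%).

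**Conclusion.** The point holds as a gap in what the plan will report. The one planned safety comparison has little power for modest excesses, cannot be computed without events, and comes with no estimate. At 53 per arm the data could be compatible with an excess of 6.8 points at 0 v 0, or 13.8 points at 3 v 1, with nothing in the planned output to say so.

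The power figures and the chances of zero events rest on assumed rates. The interval limits depend only on the counts shown and the arm size.

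Two stronger readings are not supported. False-positive error is not inflated in any way that matters. And it would overstate the case to say that a null result excludes nothing: 0 v 0 excludes an excess above about 7 points. This is an inexpensive improvement to the safety reporting of a pilot trial; it does not touch the primary analysis.

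**What to change.** In 10.3 and 16.3, replace the chi-square sentence with text to this effect: the main safety result is the number of participants with an adverse event in each arm and the TOME-minus-Control risk difference with its 95% Miettinen-Nurminen score interval. State the denominator (all randomized, or those assessed at Week 3) and show both numbers by arm. If a p-value is kept, name the test and label it secondary. Add that a non-significant result, or one that cannot be computed, will not be reported as absence of harm.

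This takes a few sentences in two sections and a few lines of code, with no new data and no change to sample size. The downside is that the intervals will be wide and will be seen to be wide. The change does not raise the trial's ability to detect harm; it makes the limit of that ability visible.
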